12.4 Demographics and Baseline Characteristics

Demographic variables and other baseline characteristics will be summarised. These summaries will be produced for the efficacy population and the safety population. Both baseline in the ePHex study and second baseline in the ePHex-OLE study will be described. Baseline distributions will be examined and any potential impact of differences found will be evaluated and discussed. Demographics and baseline characteristics will also be described for patients included in the FAS of the ePHex study but not participating in the ePHex-OLE study.

12.5 Primary Endpoint

Kidney function measurements of eGFR will be calculated primarily based on the creatinine - based "Bedside Schwartz" equation (2009) (for children below 18 years of age) and the creatinine - based CKD-EPI equation (2009). For subjects reporting age 18 to 23 years old at screening visit 1 of ePHex the mean of child and adult equations will be used. Subjects eGFR will be calculated using the same equation used at the ePHex study baseline throughout the study. Supportive summaries may use alternative eGFR equations.

Change from baseline in kidney function (eGFR) over time (including both the ePHex and the ePHex-OLE study) will be calculated as each visit value minus the value at baseline (ePHex). Description of eGFR and change from baseline in eGFR values after 24 months of open-label Oxabact treatment will be considered the primary analysis, although 12 months will also be presented. Graphical presentations of the eGFR data over time will therefore be done based on the observed data per individual patient as well as scatter and/or spaghetti plots.

In addition, to describe if Oxabact treatment has a similar effect during the first 12 and 24 months in the 0 - 0 and P - 0 groups, change from second baseline in eGFR over time will be summarised as above.

Additional description of the data will be provided including summaries and graphs of observed eGFR mean values (mean, SD) and mean change from baseline and/or second baseline over time.

12.5.1 Change from Baseline in eGFR Supportive Analyses MRMM

A supportive additional analysis of the data may also be performed, whenever possible, using Mixed Effect Repeated Measures Model (MRMM) analysis based on the FAS with a model including fixed effect factors: treatment group (0 - 0; P - 0), baseline stratification factors at randomisation (PH type 2/3, not PH type 2 or 3 and baseline urinary oxalate excretion $\leq 1.87 \text{ mmol}/24\text{h}/1.73 \text{ m}^2$, not PH type 2 or 3 and baseline urinary oxalate excretion $\geq 1.87 \text{ mmol}/24\text{h}/1.73 \text{ m}^2$), week, and week-by-treatment interaction, and the following fixed effect covariates: baseline eGFR value.

An autoregressive of order 1 (AR (1)) variance covariance matrix will be used for the within subject variation in the MRMM model. In case there is a convergence problem the following variance covariance matrix structures will be used in the order of 1) unstructured, 2) Toeplitz, and 3) compound symmetry (CS). The first (co)variance structure which does not have convergence problem will be the one used for the analysis.

A descriptive comparison will be presented at 12 and 24 months in change from baseline between 0 – 0 and P – 0 treatment groups as measured by the treatment effect factor. Results will be summarised including LS mean change from baseline in eGFR at months 12 and 24 (SE) in both treatment groups along with treatment group difference (LS mean difference) and corresponding 95% confidence interval. The same results will be presented also for the other timepoints.

To describe if Oxabact treatment has a similar effect during the first 12 and 24 months in the O-O and P-O groups, a second MRMM analysis on change from baseline in eGFR in the O-O group and change from second baseline in the P-O group based on the FAS will be used with a model including fixed effect factors: treatment group (O-O; P-O), week, and week-by-treatment interaction, and the following fixed effect covariates: baseline eGFR (baseline for the O-O group and second baseline for the P-O group).

12.5.2 Change from Baseline in eGFR Supportive Analyses

A secondary method of analyses, corresponding to the MRMM above, will be done using an ANCOVA model with treatment group, baseline/second baseline stratum, and baseline/second baseline as covariates and change from baseline/second baseline in eGFR at 12 and 24 months as a dependent variable. Supportive analyses based on AUC may also be performed and further described in the SAP.

12.5.3 Change from Baseline in eGFR Supportive Summaries of Slopes

Another description of the data based on slopes will be provided. For each patient, a separate regression analysis will be calculated for eGFR observed values over time and individual subject slopes identified. Slopes will be then summarised primarily with descriptive statistics. In order to describe differences a non-parametric analysis is proposed, the Wilcoxon rank-sum test may be used for comparisons, medians and quartiles can be provided, estimates for the median of groups differences or within group differences, Hodges-Lehmann approach estimate of location shift and the 2-tailed Moses 95% confidence intervals.

12.6 Key Secondary Endpoints

12.6.1 Total Plasma Oxalate

Change from baseline in total plasma oxalate concentration will be analysed similar to the primary endpoint. Total Pox observed minimum and maximum post baseline values and change from baseline will also be summarised and plotted. Additionally, a combined plot for key secondary endpoint total plasma oxalate and primary endpoint eGFR over time will be created using a double-axis display. This plot will be created for

each patient, but also a summary plot presenting both parameters' mean values over time per treatment group will be made.

12.6.2 Kidney Stone Events

Frequency of kidney stone events after 12 and 24 months of treatment. Kidney stone events are defined as:

- Subject- or investigator-reported symptoms, or
- Stone passages or removals, or
- Increase in the number of kidney stones as assessed by ultrasound

Kidney stone events after 12 and 24 months of open-label Oxabact treatment will be summarised using descriptive statistics. Incidence rates of kidney stone events (defined as the number of events divided by the total person-years) will be calculated along with the number of subjects with a stone event. Risk ratio and risk difference between the two treatment groups will be presented in combination with a 95% CI.

Time lost at work or school due to kidney stone events will be summarised.

12.7 Other Endpoints

- Change from baseline in myocardial function parameters as measured by Speckle Tracking and traditional echocardiography) will be summarised descriptively over time after 12 and 24 months of open-label Oxabact treatment.

 STE results will be evaluated over time for global longitudinal strain, including segmental changes, short-axis myocardial function, rotational displacement and apical sparing patterns. Traditional echocardiographic parameters will also be evaluated over time (e.g. Ejection Fraction, End Diastolic Volume, e/é, e/a, Left Ventricular End Diastolic Dimension, Fractional shortening, Tricuspid Regurgitation by Doppler as an indicator of right ventricular/pulmonary pressure.). A positive treatment effect would be an improved myocardial function based on the above-mentioned parameters, decreased global longitudinal strain, improved rotational displacement and reduced/removed apical sparing pattern. Change from baseline in free plasma oxalate after 12 and 24 months of open-label Oxabact treatment will be described similar to the primary endpoint.
- Change from baseline in urinary oxalate excretion after 12 and 24 months of open-label Oxabact treatment will be described.
- Grade of nephrocalcinosis after 12 and 24 months of open-label Oxabact treatment will be summarised. Grade of nephrocalcinosis will be assessed by ultrasound images using grades 0-3.
- Number of *O. formigenes* during the study will be summarised over time. Summaries will present both observed and change from baseline values overall and by genotype (genotype 1, and genotype 2). In the P O group, change from second baseline will be used instead. The association between *O. formigenes* in

- stool and total plasma oxalate concentration will be evaluated using graphical displays.
- Change from baseline in Quality of Life scores as measured by SF36V2 or CHQ/PF50 questionnaires, depending on age, will be summarised over time in the two treatment groups.
- Change from baseline after 12 and 24 months of open-label Oxabact treatment in markers for renal function, renal tubular capacity and inflammation in urine and plasma will be described. Remaining time-points during the study will be presented as supportive.

12.8 Subgroup Analysis

The results of the study will be presented primarily with descriptive individual data graphically presented over time and therefore no additional subgroup analyses will be needed for these. For summaries and/or any other analyses presented the following subgroups will be considered, only if there is sufficient sample size and for the following endpoints: eGFR, total and free plasma oxalate concentration, 24-hour urinary oxalate excretion, stone events, absolute count of *O. formigenes* per gram in stool, speckle tracking and traditional echocardiography). The subgroups are:

- Subjects with a baseline 24-hour urinary oxalate excretion above and equal to or below 1.87 mmol/L/24h/1.73 m² respectively (mean of the two values during screening/baseline of the ePHex study).
- Subjects above or equal to and below 18 years of age at baseline of the ePHex study.
- Subjects with a baseline eGFR above or equal to and below 60 ml/min/1.73m² respectively (mean of the obtained values during screening/baseline calculated by the creatinine based "Bedside Schwartz" equation (2009) for children below 18 years of age and the creatinine based CKD-EPI equation (2009) for adults).
- Race.
- Gender.
- Progressors and non-progressors based on historic eGFR (i.e. eGFR prior to treatment start in the ePHex study).
- Type of PH

12.9 Safety

Adverse events will be categorised by System Organ Class (SOC) and Preferred Term from MedDRA. Safety data will be summarised for the overall study population SAF and also according to the actual treatment received in the ePHex study 0-0 and P-0. AEs will be considered to be treatment emergent if the event occurs on or after the first administration of open label Oxabact treatment and up to 4 weeks after the last dose date of open-label Oxabact treatment of the ePHex-OLE study.

The incidence of AEs will be summarised using descriptive statistics, by SOC, preferred term and severity grade (CTCAE) for all treatment emergent, serious, treatment-related, and serious treatment-related AEs. Summaries will be provided separately for AEs leading to investigational product discontinuation and deaths (severity grade 5).

Changes in safety laboratory parameters, vital signs and physical examinations will also be summarised. Graphical representations may also be presented for parameters of interest. Listings of SUSARs, AEs and SAEs will be provided along with narratives.

12.10 Other Data

Subjects starting dialysis will be described.

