formal statistical testing will be done and therefore no correction for multiple comparisons will be necessary in the present analyses.

An interim analysis summarising both efficacy and safety will be performed when all subjects enrolled in the ePHex-OLE study have 12 months data.

Analysis of the Primary Endpoint

Graphical presentations of eGFR over time, observed and change from baseline values, will be done per individual patient as well as scatter and/or spaghetti plots.

Description of the data will also be provided including summaries and graphs of observed eGFR mean values (mean, standard deviation (SD)) and mean change from baseline and/or second baseline over time.

In addition, to describe if treatment with Oxabact presents a similar effect during the first 12 and 24 months in the (Oxabact – Oxabact (O - O) and Placebo – Oxabact (P – O)) groups, change from second baseline in eGFR over time will be presented as above.

As supportive analyses, and performed only if there is sufficient sample size, a MRMM will be used with a model including the following fixed effect factors: treatment group (0-0; P-0), baseline stratification factors at randomisation (PH type 2/3, not PH type 2 or 3 and baseline urinary oxalate excretion $\leq 1.87 \text{ mmol}/24\text{h}/1.73 \text{ m}^2$), not PH type 2 or 3 and baseline urinary oxalate excretion $\geq 1.87 \text{ mmol}/24\text{h}/1.73 \text{ m}^2$), week, and week-by-treatment interaction, and the following fixed effect covariate: baseline eGFR value.

A second MRMM analysis will be used to evaluate change from Oxabact treatment initiation in eGFR to describe if Oxabact treatment present a similar effect during the first 12 and 24 months.

As a second analytical method approach will be provided as supportive analyses (i.e. Analysis of Covariance (ANCOVA) and/or Area under the curve (AUC) to evaluate the changes at 12 and 24 months. In addition, slopes will be calculated and summarised.

Data descriptions wil be based on observed data. Reasons for missing data and study drop-out will be described and evaluated. For the statistical analyses, and if sufficient data is available multiple imputations (MI)/last observation carried forward (LOCF) methods may be used to impute missing data, and if possible missing not at random (MNAR) may be evaluated with a pattern-mixture model (PMM).

Key secondary endpoints

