6 INVESTIGATIONAL PLAN

6.1 Background and Rationale

This study is an open-label, single arm, multi-centre study to evaluate the efficacy and safety of the long-term use (two years of open-label Oxabact treatment) of OC5 (*O. formigenes*) to stabilise/improve kidney function, stabilise/reduce plasma oxalate concentration, and to reduce oxalate deposits in PH patients. Included subjects will be the subjects who underwent treatment (administered either Oxabact or placebo) in the ePHex study and consented to participate in the ePHex-OLE study. At the start of the ePHex study, subjects had maintained renal function but with an eGFR below the lower limit of the normal ranges (<90 ml/min/1.73 m²) and a total plasma oxalate concentration ≥ 10 µmol/L at baseline. These criteria will not be re-tested for inclusion into the ePHex-OLE study protocol.

It is hypothesised that daily administration of *O. formigenes* facilitates the secretion of endogenously produced oxalate via the GI tract. Enteric elimination of oxalate may help to reduce oxalate deposits and eventually decrease the plasma oxalate level, thereby improving eGFR and kidney function as well as progression of myocardial function.

A natural history study in PH patients included in the Rare Kidney Stone Consortium (RKSC) Registry (Zhao et al., 2016) studied the key determinants for renal outcome in this patient population. The subjects included in the analysis had a mean eGFR of 73 ml/min/1.73 m². During a median follow-up of 3.9 years (1.0, 12.8), 20% of subjects developed ESRD. The most important progression factors for kidney deterioration in subjects with PH from this registry study are detailed in Table 4.

Table 4 Factors Univariately Associated with Incident ESRD among PH Patients without ESRD at Diagnosis

Variable	Hazard Ratio (95% CI)	p-value
PH1	13.17 (3.19-54.38)	<0.001
Age at Diagnosis	1.02 (1.00 to 1.04)	0.02
Uox, mmol/1.73 m ² per 24h	1.13 (0.94 to 1.37)	0.20
Uox, mmol/1.73 m ² per 24h (Q4)*	3.40 (1.40 to 7.90)	0.01
eGFR, ml/min per 1.73 m ²	0.96 (0.94 to 0.99)	0.002

^{*}Q4: Quartile 4 related to an urinary oxalate excretion of >1.87 mmol/1.73 m² per 24hr

Scientific evidence in support of eGFR change

The recently published KHI consensus paper on "Endpoints for clinical trials in Primary Hyperoxaluria" highlights the importance of preserving renal function and summarises the available literature on the rate of kidney function decline in patients with PH (Milliner *et al*, 2020):

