7.4 Subject Withdrawal Criteria

If a subject fails to return for a scheduled study visit, the investigator will make a reasonable effort to contact the subject and determine why the subject failed to return and to schedule a new study visit. Any information obtained during this contact will be documented in the study records.

A study subject will be discontinued from treatment in the study if:

- Any clinically significant AE, laboratory abnormality, illness, or other medical condition or situation occurs such that continued participation in the study would not be in the best interest of the subject.
- OxThera or the Principal Investigator in consultation with OxThera may discontinue the subject at any time for medical and/or administrative reasons.
- The Prinicpal Investigator in consultation with OxThera may discontinue the subject in case of a major protocol violation.
- The subject requires dialysis.

Protocol OC5-OL-02, Confidential

Any subject who withdraws prematurely from the study treatment will be asked to complete all study assessments scheduled for the month 12 or 24 visit at the time of withdrawal and will be followed for safety for 4 weeks after the last intake of study drug. Subjects will provide a stool sample 4 weeks after end of treatment.

Patients who withdraw consent from participating in the study at any time will end the study. They will not have any further assessment and no further study data will be collected.

For any subject who has withdrawn, the date of withdrawal from the study and the reason for withdrawal from treatment and from the study will be recorded in the source data and eCRF.

Withdrawn subjects will not be re-entered into the study.

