7.6 Statistical analysis primary and secondary endpoints

7.6.1 Primary endpoint

The primary efficacy endpoint is the change from baseline in kidney function (eGFR) after 12 and 24 months of open-label Oxabact treatment. The primary endpoint will be presented using the FAS population.

The primary analysis will be based on the 24-month data and using the baseline of the ePHex as primary baseline, while other time-points presented will be considered as supportive. A second analysis is done using the baseline of ePHex-OLE for the ePHex placebo subjects as baseline.

Change from baseline in kidney function (eGFR) will be calculated at each visit, using the two different baselines. Summary statistics of the measurements will be presented on a per-visit basis. Presentations will be per treatment group and overall.

To visualize the effects through time graphically, the following plots will be created:

- Individual plots will be created to visualize the course of eGFR values through time (including the ePHex values, as applicable). Both the actual values as well as change from baseline values will be presented.
- Mean \pm SE will be created to visualize the course of eGFR values through time (including the ePHex values, as applicable). Both the actual values as well as change from baseline values will be presented for the overall group and for both treatment groups, preferably in the same plot.
- Spaghetti plots per treatment group of the actual values will be created to visualize the group course of eGFR through time, using the same y-axis for visual comparison between groups. No spaghetti plots will be created for change from baseline. One plot will be created, using colors to discriminate both treatment groups (which combined will show the overall group).
- A plot presenting LS estimates \pm SE will be created, based on the mixed-effect repeated measures model stated below.

A statistical analysis will be performed using a mixed-effect repeated measures model (MRMM) on the change from baseline value at 12 and 24 months, with the following independent variables: treatment group, baseline eGFR value, time and time*treatment group interaction. If the assumption of normality is violated, a log transformation will be applied first (and a back transformation will be done on the results). SAS PROC MIXED (with the REML default) will be used for the analysis. The basic SAS code will be as follows.

```
proc mixed data=...;  
  class usubjid <time>;  

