As a sensitivity analysis for the primary endpoint, the same model will be used after applying a multiple imputation (MI) method for missing data under the missing at random assumption (MAR). Missing data patterns and covariates related to the missing data patterns will be examined and described. A total of 10 multiple imputations will be generated using predicted mean matching based on a monotone regression (in case the missing data pattern is monotone) or on a fully conditional specification regression (in case the missing data pattern is arbitrary and non-monotone). The predicted mean matching method imputes an observed value which is closest to the predicted value from the simulated regression model for each missing value. It ensures that imputed values are plausible and might be more appropriate than the regression method if the normality assumption is violated. The regression model will condition on observed values of the primary outcome measured at other time points (including baseline measurements) and possible other covariates that are related to the missing data pattern and/or primary endpoint.

The mixed-effect repeated measures model described above will be applied to each imputed dataset separately. The estimated parameters will be pooled using Rubin's combining rules. Only the primary comparisons at 12 and 24 months will be analysed using this approach.

The analysis above will be done under the assumption of missing at random (MAR). Since it concerns a supportive analysis of the descriptive statistics, no further analysis will be done to assess the robustness of the primary analysis to possible deviations from the missing at random (MAR) assumption.

As a secondary method of analyses corresponding to the MMRM above will be done using an ANCOVA model with treatment group, baseline/second baseline as covariates and change from baseline/second baseline in eGFR at 12 and 24 months as a dependent variable.

An additional statistical analysis using MRMM will be employed to evaluate the change in eGFR when on Oxabact treatment for a period of 12 months or 24 months, depending on when the subject actually received Oxabact for the first time (for O – O this is the start of treatment during the ePHex study, for P – O this is the start of treatment during the current study).

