8 CHANGES FROM PROTOCOL AND OTHER RELEVANT REMARKS

The descriptive statistics on percent change from baseline in total plasma oxalate concentration, on subjects achieving 'near-normalization' of total plasma oxalate concentration (<10 µmol/L), and on the shifts to minimum and maximum values for total plasma oxalate concentration were not mentioned in the protocol, but added as these were considered relevant in the ePHex study.

Subgroup analysis based on type of PH (as per randomization for ePHex) will not be conducted due to the expected insufficient number of subjects in the subgroups.

The sensitivity analysis for the MRMM for eGFR will be done under the assumption of missing at random (MAR). Since it concerns a supportive analysis of the descriptive statistics with a small sample size, no further analysis will be done to assess the robustness of the primary analysis to possible deviations from the missing at random (MAR) assumption, and therefore the pattern-mixture analysis is removed from the SAP.

Furthermore, the regression analysis to determine slopes for eGFR, and the summary table and statistical thereof is excluded from the SAP, considering slopes are already determined based on a MRMM. Any apparent differences in slopes can best be assessed based on the individual slope results of the MRMM analyses and viewing the spaghetti and mean plots.

Any post-hoc analyses or changes in regards to the statistical analysis plan when performing the final analyses after data base lock, will be captured in a Note to File and used for the relevant sections in the clinical study report.

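### No rule says how dialysis, death or the withdrawal eGFR enters the month-24 eGFR summary, so the observed mean may omit the worst renal outcomes

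*Protocol*

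**What the plan says.** - Stopping treatment: Protocol 7.4 lists "The subject requires dialysis" among the reasons for ending study treatment. Anyone who stops early "will be asked to complete all study assessments scheduled for the month 12 or 24 visit at the time of withdrawal". Four weeks of safety follow-up and a stool sample come after that. No later efficacy visits are described.
- Primary result: SAP 7.6.1 states "The primary analysis will be based on the 24-month data and using the baseline of the ePHex as primary baseline". The protocol synopsis adds "Data descriptions wil be based on observed data", and Protocol 12.5 treats the 24-month description as the primary analysis.
- Dialysis in the analysis: Protocol 12.10 has one sentence, "Subjects starting dialysis will be described". The SAP has no table, listing or eGFR rule for dialysis, and SAP 8 does not list this among its changes from the protocol.
- Missing data: Protocol 12.11 offers LOCF, multiple imputation and a pattern-mixture model as options. SAP 7.6.1 keeps the repeated-measures model (MRMM), an ANCOVA, and multiple imputation under missing at random (MAR). It says that "no further analysis will be done to assess the robustness of the primary analysis to possible deviations from the missing at random (MAR) assumption". SAP 8 records the reasoning and concludes "therefore the pattern-mixture analysis is removed from the SAP". LOCF does not appear in the SAP.

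**The concern.** Kidney failure is the outcome that most directly contradicts stable or improved kidney function, and it is also what ends a subject's treatment and scheduled eGFR visits. A month-24 mean of observed values is then a mean over subjects who did not reach that outcome, unless the withdrawal value is counted at month 24. Neither document says whether it is.

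MAR is least plausible for this kind of missingness. Protocol 6.1 describes a decline that steepens sharply in the last years before end-stage disease, so values seen before dialysis under-predict the later loss. Protocol 6.3.2 also asks subjects not to attend during an acute kidney injury or stone event, while the consensus text quoted in 6.1 says that such events can precipitate kidney failure. Some of the lowest values may therefore never be taken.

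At stake is whether the reported month-24 change can be read as the course of kidney function in the whole group, and whether the O-O and P-O groups can be compared if one loses more subjects to dialysis than the other.

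**Working it through.** **The plan's own figures.** Attrition in Protocol 12.2: 16 × 0.75 = 12 and 12 × 0.75 = 9, as stated. Table 11 reproduces with 8 per group, a two-sided normal approximation and the mean of m equally correlated measurements. The variance factor is (1 + (m - 1) × 0.70)/m. The documents do not give m. With m = 18 the factor is 12.9/18 = 0.7167, and all 12 cells match to within 0.00001 (0.97601 for difference 5, SD 3). The point does not rest on an arithmetic error in the plan.

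**How many events to expect (illustrative).** Protocol 6.1 reports that "20% of subjects developed ESRD" during a median follow-up of 3.9 years. Reading this as a constant hazard (an assumption):
- hazard = -ln(0.80)/3.9 = 0.0572 per year
- two-year risk = 1 - exp(-2 × 0.0572) = 10.8%
- expected cases = 18 × 0.108 = 1.9, using the 18 included subjects in SAP 2.4 (1.7 with 16)
- chance of no more than one case among 18 = 0.892^18 + 18 × 0.108 × 0.892^17, about 41%

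**Effect on the mean change at month 24 (36 months from ePHex baseline).** Assume subjects without dialysis lose 1 mL/min/1.73 m² per year, so 3 in total. This lies within the rates of 0.4 to 1.7 per year quoted in Protocol 6.1. Assume each dialysis subject loses 9 per year, the late slope in the same section, for 2 or 3 years, so 18 to 27. With k events among 18:

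mean = ((18 - k) × (-3) + k × (-L))/18, with L = 18 or 27

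| Events | L = 18 | L = 27 | Mean without them |
|---|---|---|---|
| 0 | -3.0 | -3.0 | -3.0 |
| 1 | -69/18 = -3.8 | -78/18 = -4.3 | -3.0 |
| 2 | -84/18 = -4.7 | -102/18 = -5.7 | -3.0 |

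In one group of 8, as in the planned 1:1 split of 16, leaving out one such subject moves the group mean by 15/8 = 1.9 to 24/8 = 3.0. The planned group difference is 5.

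**Does the MAR model repair this?** A simulation used 16 subjects in one group, AR(1) correlation 0.7, SD 3 and 1,500 replicates. The others declined by 0.822 per year (the early slope in Protocol 6.1). Two dialysis subjects declined by 9 per year during the extension and had no withdrawal value at month 24. Entries are mean month-24 changes.

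| Last visit of the two subjects | Full data | Observed | MRMM | Share recovered |
|---|---|---|---|---|
| Month 12 | -4.55 | -2.51 | -2.76 | 0.25/2.04 = 12% |
| Month 18 | -4.51 | -2.48 | -3.23 | 0.75/2.03 = 37% |

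One or three such subjects, or SD 5, give similar shares. The model was simpler than the SAP's: known covariance, and no treatment or baseline term.

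**The case against.** The strongest reply is that these subjects do not vanish. Their pre-dialysis values stay in the individual profiles and spaghetti plots, which the protocol puts first, and in the earlier visit summaries and the MRMM. Protocol 7.4 collects an eGFR at withdrawal. If that value is analysed as month 24, the poor result enters the primary summary. The mapping may be in SAP Addendum 1, which is not among the documents. SAP 7.4.2 tabulates reasons for non-completion by group and lists withdrawal reasons by subject, and SAP 7.6.1 describes missing-data patterns. All of this stands. A reader might infer that dialysis subjects drop out of the eGFR results altogether, and the documents do not support that.

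A reader might also infer that the SAP withdrew a firm commitment. It did not. Protocol 12.11 offered the pattern-mixture model only if needed and feasible, SAP 8 discloses its removal, and a pattern-specific model could hardly be fitted with 18 subjects. But the reason given, that the model is only supportive, leaves the descriptive month-24 mean without any check of its own.

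The size is also open to challenge. A three-year risk (1 - exp(-3 × 0.0572) = 15.8%, or 2.8 of 18) is tempting. However, entrants must have completed ePHex, normally 52 weeks of treatment (Protocol 6.3.1), so only the two extension years apply. The late slope comes only from patients who reached end-stage disease, and Protocol 6.1 warns that it does not describe all patients. These objections limit the figures. They do not supply the missing rule.

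**Conclusion.** The point holds as a gap in the endpoint definition. Neither document places dialysis or death in the month-24 eGFR summary or assigns the withdrawal eGFR to a visit. The SAP also omits the protocol's dialysis description and has no analysis beyond MAR. The observed month-24 mean may therefore omit the worst renal outcomes and look too favourable.

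Under the stated assumptions the overstatement is 0.8 to 1.3 mL/min/1.73 m² with one event, 1.7 to 2.7 with two, and nothing with none. The number of dialysis starts in the trial is not given. The range rests on a constant hazard, on registry rates applying to this population, and on all other subjects being observed at month 24, although the plan expects 25% drop-out per year.

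The documents do not support a claim that the bias favours Oxabact in the group comparison. Both groups take Oxabact throughout the extension, and the direction depends on which group has more events.

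**What to change.** In SAP 7.6.1:

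1. State which visit the withdrawal eGFR from Protocol 7.4 is assigned to. Keep it if it was drawn before dialysis started. Do not use a creatinine-based eGFR drawn after dialysis start as a measure of native function.
2. Show the number of subjects with dialysis or death, by group, beside the month-12 and month-24 eGFR tables. This also carries Protocol 12.10 into the SAP.
3. Add one supportive non-MAR summary at months 12 and 24. Give subjects with dialysis or death by that visit the worst rank, and report medians and a Hodges-Lehmann O-O versus P-O difference, an estimator already named in Protocol 12.5.3. Run it when the full SAP is followed (SAP 7.1, option 1), and reword the sentence that rules out any check on MAR.

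A version that assigns a fixed low eGFR from dialysis start is optional, since the value is a convention. No change to the rule for stopping treatment is proposed.

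The cost is SAP wording and one or two extra tables. The drawback is that the rank summary is not in mL/min/1.73 m² for the affected subjects.
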